5.4. Secondary Endpoint(s) Analysis

5.4.1. Key Secondary Endpoint

5.4.1.1. Definition of Endpoint

A relapse is defined by any of the following:

- a) Worsening of depressive symptoms as indicated by MADRS total score ≥22 confirmed by 1 additional assessment of MADRS total score ≥22 within the next 5 to 15 days. The date of the second MADRS assessment will be used for the date of relapse.
- b) Any psychiatric hospitalization for
 - a. worsening of depression
 - b. suicide prevention or due to a suicide attempt

For any of these events, the start date of hospitalization will be used for the date of relapse.

c) Suicide attempt, completed suicide, or any other clinically relevant event determined per the investigator's clinical judgment to be indicative of a relapse of depressive illness, but for which the participant was not hospitalized. The onset of the event will be used for the date of relapse.

In case more than 1 of the relapse criteria are met, the earliest date will be defined as the date of relapse for that participant.

The key secondary endpoint is remission at Week 8 visit (ie, MADRS total score of ≤ 10 at the end of Week 8) *and* no relapse within the consecutive 24 weeks until the end of the prospective observation period at Week 32 visit.

5.4.1.2. Estimand(s)

Key Secondary Trial Objective: to evaluate the efficacy of flexibly dosed esketamine nasal spray compared with quetiapine XR, both in combination with a continuing SSRI/SNRI, in achieving remission at the Week 8 visit *and* having no relapse within the consecutive 24 weeks until the end of the prospective observation period at Week 32 visit in participants who have treatment resistant MDD with a current moderate to severe depressive episode.

Estimand Scientific Question of Interest: What is the proportion of participants considered to have benefited from esketamine versus quetiapine XR for the pre-specified duration (32 weeks), administered in combination with a continuing SSRI/SNRI?

Study intervention:

- Flexibly dosed esketamine nasal spray in combination with a continuing SSRI/SNRI
- Quetiapine XR in combination with a continuing SSRI/SNRI.

Population: Participants

- 18 to 74 years of age (inclusive) with treatment resistant MDD
- on a current antidepressive treatment that includes an SSRI/SNRI that resulted in nonresponse, but the participant shows signs of minimal clinical improvement
- must have documented nonresponse within the current moderate to severe depressive episode to at least 1 but not more than 5 different, previous consecutive treatments with ADs taken at an adequate dosage for an adequate duration of at least 6 weeks, and that each prior AD treatment did not produce any significant improvement
- must have been treated with at least 2 different antidepressive substance classes among the failed treatments in the current depressive episode.

Variable: Week-32-response (binary variable), where week-32-response is defined as a participant achieving remission at the Week 8 visit (defined as a MADRS total score of ≤ 10) *and* having no relapse within the consecutive 24 weeks until the end of the prospective observation period at Week 32 visit, who does not:

- discontinues (any component of) study intervention, or
- withdraws from the study.

Summary measure (population-level summary): Difference in proportions.

Intercurrent Events	Strategy for Addressing Intercurrent Events and Its Description
Discontinuation of (any component of) study intervention for any reason	Composite Strategy : A participant with this intercurrent event is considered as a non-responder after this event, the occurrence of this intercurrent event being captured in the variable definition
Withdrawal from the study	Composite Strategy: Same as above

Intercurrent events and their corresponding strategies:

In the main analysis, for subjects who do not have an available MADRS result at the Week 8 visit but did not discontinue study intervention or withdraw from study before Week 8, LOCF of MADRS will be applied at Week 8. In a sensitivity analysis, these subjects will be considered to not be in remission at Week 8.

5.4.1.3. Analysis Methods

The efficacy analysis of data will be based on the full analysis set. Statistical analysis test will be conducted at a two-sided 0.050 level of significance.

The rate of remission at the Week 8 visit *and* having no relapse within the consecutive 24 weeks until the end of the prospective observation period at Week 32 visit will be tested between study intervention arms using a Cochran-Mantel-Haenszel (CMH) chi-square test adjusting for age (18 to 64 years [inclusive]; 65 to 74 years [inclusive]) and total number of treatment failures (2; 3 or more). The estimate of the treatment difference in proportions, the odds ratio and their 95% CI will be reported. In the main analysis, the variables age and number of treatment failures will be based on CRF data. A sensitivity analysis will be performed using IXRS data.

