9.1. Statistical Hypotheses

The primary hypothesis of this study is that among participants who have treatment-resistant MDD with a current moderate to severe depressive episode, the proportion of participants achieving remission at the Week 8 visit is greater in participants treated with flexibly dosed esketamine nasal spray than in participants treated with quetiapine XR, both administered in combination with a continuing SSRI/SNRI.

The major secondary hypothesis of this study is that among participants who have treatment-resistant MDD with a current moderate to severe depressive episode, the proportion of participants who achieved remission at the Week 8 visit and remain relapse-free through the Week 32 visit is greater in participants treated with esketamine nasal spray than in participants treated with quetiapine XR, both administered in combination with a continuing SSRI/SNRI.

Both the primary and major secondary endpoint will be analyzed using a non-responder imputation (NRI) approach, meaning that participants discontinuing study intervention will be considered as

having a negative outcome (non-remission for the primary endpoint, non-relapse-free-remission for the key secondary endpoint).

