9.2. Sample Size Determination

For the primary endpoint, the assumptions are that the rate of remission for completers at the Week 8 visit is 50% in the esketamine arm and 35% in the comparator arm, and that the rate for participants who discontinue study intervention between baseline and the Week 8 visit is 17.5% in both treatment arms (to be imputed as non-remitters). Combining these assumptions leads to an estimated remission rate at the Week 8 visit in NRI analysis of 41.25% in the esketamine arm and 28.88% in the comparator arm. With a power of 90%, a 2-sided significance level of 0.05 and using chi-square test, a sample size of 311 participants per arm (622 participants in total) is needed to detect the difference between the study intervention arms.

For the key secondary endpoint, among participants who achieve remission at the Week 8 visit, a relapse rate of 30% is assumed for both study intervention arms and rates for participants who discontinue study intervention between the Week 8 and Week 32 visits (to be imputed as non-relapse-free after remission) is assumed to be 10% for the esketamine arm and 20% for the comparator arm.^{2,7,24} Combining these assumptions leads to an estimated rate of relapse-free after remission at the Week 32 visit in NRI analysis of 25.99% in the esketamine arm and 16.17% in the comparator arm. With a power of 80%, a 2-sided significance level of 0.05 and using a chi-square test, a sample size of 270 randomized participants per arm (540 participants in total) is needed to detect a difference between the study intervention arms.

When combining the 2 calculations above, a sample size of 311 participants per study intervention arm (622 participants in total) is needed to detect the difference between the study intervention arms with both a power of at least 90% on the primary endpoint and a power of 80% on the key secondary endpoint.

Randomization will be stratified by age (18 to 64 years [inclusive]; 65 to 74 years [inclusive]) and total number of treatment failures (2; 3 or more [inclusive of current antidepressive treatment at screening used to determine eligibility]).

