9.4.2. Efficacy Endpoints

The efficacy analyses of data will be based on the full analysis set defined in Section 9.3.

The rate of remission at the Week 8 visit (primary endpoint) and the rate of remission at the Week 8 visit without relapse up to the Week 32 visit (key secondary endpoint) will be tested between study intervention arms using a Cochran-Mantel-Haenszel (CMH) chi-square test adjusting for age (18 to 64 years [inclusive]; 65 to 74 years [inclusive]) and total number of treatment failures (2; 3 or more). Participants will be considered as having a positive outcome on relapse-free after remission if they are in remission at the Week 8 visit and do not experience any relapse between the Week 8 and Week 32 visits. All other cases (participants not achieving remission at the Week 8 visit, or participants achieving remission at the Week 8 visit but experiencing a relapse between the Week 8 and Week 32 visits) will be considered as having a negative outcome. Both the primary and key secondary endpoints will be analyzed using a NRI approach as defined in Section 9.1. In sensitivity analyses, for participants who stopped study intervention, but are still followed in the study, no imputation will be performed, and their observed status will be used for the analyses.

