2. STATISTICAL HYPOTHESES

The primary hypothesis of this study is that among participants who have treatment-resistant MDD with a current moderate to severe depressive episode, the proportion of participants achieving remission at the Week 8 visit is greater in participants treated with flexibly dosed esketamine nasal spray than in participants treated with quetiapine XR, both administered in combination with a continuing SSRI/SNRI.

The key secondary hypothesis of this study is that among participants who have treatment-resistant MDD with a current moderate to severe depressive episode, the proportion of participants who achieved remission at the Week 8 visit and remain relapse-free through the Week 32 visit is greater in participants treated with esketamine nasal spray than in participants treated with quetiapine XR, both administered in combination with a continuing SSRI/SNRI.

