5.5. Supportive Secondary Endpoint(s)

5.5.1. General Analysis Methods

For continuous/ordinal parameters (eg, MADRS, CGI-S, PHQ-9, EQ-5D-5L, SF-36, SDS, WPAI:D) descriptive statistics of the score or values and change from baseline will be provided for each study visit during the study for the full analysis set. For CGI-C descriptive statistics of the score will be provided for each study visit during the study by study intervention for the full analysis set. Summaries of both observed and last observation carried forward (LOCF) data will be presented. The change from baseline at each visit will be analyzed using a mixed model for repeated measurements based on observed cases. The model will include baseline score as a covariate, and study intervention, stratification factors (age [18 to 64 years (inclusive); 65 to 74 years (inclusive)] and total number of treatment failures [2; 3 or more]), visit, and visit-by-study intervention interaction as fixed effects applying an unstructured covariance matrix. In case of issue with convergence of the model, alternative structures of variance-covariance matrix will be tested. The change from baseline at each visit will also be analyzed using an analysis of covariance model including LOCF data with factors for treatment, stratifications factors (age [18 to 64 years

(inclusive); 65 to 74 years (inclusive)] and total number of treatment failures [2; 3 or more]) and baseline score as a covariate. For all model approaches, LS estimates of the treatment differences at each visit and 95% confidence intervals will be presented. Additionally, for the MMRM model, the LS mean change from baseline averaged over all visits will be presented with 95% confidence interval per treatment group. The corresponding treatment difference will be presented with 95% confidence interval and two-sided p-value.

Additionally, for scales that have a minimum clinically important difference (MCID), the proportion of participants having improved by at least the MCID will be described at each visit and compared between study interventions using CMH chi-square test adjusting for age (18 to 64 years [inclusive]; 65 to 74 years [inclusive]) and total number of treatment failures (2; 3 or more). The same analysis will be conducted for the proportion of participants who deteriorate by at least the MCID.

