6.2. Appendix 2 Changes to Protocol-Planned Analyses

The analysis of time to event endpoints as described in the protocol includes both descriptive analysis, log-rank test and Cox proportional hazards model. However, since time to relapse is an exploratory endpoint, the analysis of this endpoint will only be descriptive.

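### The primary and key secondary endpoints are each tested at the full 0.05 with no rule ordering them, so if neither effect exists the chance of a false claim for esketamine is 4.2% rather than 2.5%

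*SAP*

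**What the plan says.** Both documents give two endpoints formal status. SAP Section 2 states the primary hypothesis as directional (the proportion "achieving remission at the Week 8 visit is greater in participants treated with flexibly dosed esketamine nasal" spray than with quetiapine XR) and then adds a second: "The key secondary hypothesis of this study is that among participants who have treatment-resistant MDD". Protocol 9.1 has the same pair and calls the second one major: "The major secondary hypothesis of this study is that among participants who have treatment-resistant MDD".

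Each endpoint is sized at the full two-sided 0.05. Protocol 9.2 and SAP Section 3 give 311 per arm for the primary (90% power) and 270 per arm for the key secondary (80% power). Protocol 9.2 then combines them as one design aim, 311 per arm "with both a power of at least 90% on the primary endpoint and a power of 80% on the key secondary endpoint".

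For the analysis, Protocol 9.4.2 says in one sentence that both rates "will be tested between study intervention arms using a Cochran-Mantel-Haenszel (CMH) chi-square test". SAP 5.3.3 (primary) and SAP 5.4.1.3 (key secondary) each state: "Statistical analysis test will be conducted at a two-sided 0.050 level of significance". The key secondary has its own section, 5.4.1, outside the supportive secondary endpoints of SAP 5.5.

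No hierarchy, gatekeeping, alpha split or nominal label appears in Protocol 9.1 to 9.5, the SAP analysis sections or the SAP version history. SAP Appendix 2 lists one change from the protocol, on another endpoint: "since time to relapse is an exploratory endpoint, the analysis of this endpoint will only be descriptive".

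**The concern.** Calling one endpoint primary and the other key secondary suggests an order of testing, but a label is not a decision rule. Followed as written, the plan carries out two tests, each at 0.05, of two formally stated hypotheses. Nothing stops the second from being declared significant after the first has failed. The 5% level then holds for each test taken alone but not for the pair.

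What is at stake is how one particular result would be read: Week 32 significant, Week 8 not. Week 8 remission is a component of the Week 32 endpoint, so that pattern would be argued over. Whether it counts as a confirmatory claim or as a nominal p-value should be settled before the data are seen.

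**Working it through.** **Inputs** (Protocol 9.2, SAP Sections 1.2 and 3)
- 1:1 allocation, 311 per arm; each test two-sided at 0.05, so 0.025 in the esketamine direction (critical value 1.96).
- Week 8 remission with non-responder imputation: 0.50 × 0.825 = 0.4125 for esketamine; 0.35 × 0.825 = 0.28875 for the comparator.
- Retained to Week 32 among remitters (no relapse, no discontinuation): 0.70 × 0.90 = 0.63 for esketamine; 0.70 × 0.80 = 0.56 for the comparator.
- Key secondary rates: 0.4125 × 0.63 = 0.2599; 0.28875 × 0.56 = 0.1617.

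**Step 1. Reproduce the plan's figures.** The two-proportion chi-square formula (pooled variance, no continuity correction) gives 311 per arm for 0.4125 v 0.28875 at 90% power, and 270 per arm for 0.2599 v 0.1617 at 80% power. Both match the plan.

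**Step 2. Correlation of the two test statistics.** Every key secondary responder is also a primary responder. For nested binary endpoints with rates p1 (primary) and p2 (key secondary),

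rho = sqrt[ p2(1 − p1) / ( p1(1 − p2) ) ].

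- Comparator rates: sqrt[0.1617 × 0.71125 / (0.28875 × 0.8383)] = 0.689.
- Esketamine rates: sqrt[0.2599 × 0.5875 / (0.4125 × 0.7401)] = 0.707.

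**Step 3. Error under the global null** (no difference on either endpoint), bivariate normal. In the esketamine direction,

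P(at least one false claim) = 0.025 + 0.025 − P(Z1 > 1.96 and Z2 > 1.96).

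| Null rates | P(both significant) | At least one, favouring esketamine | Key secondary only | At least one, either direction |
|---|---|---|---|---|
| Comparator (28.88% / 16.17%) | 0.0080 | 0.0420 | 0.0170 | 0.0839 |
| Esketamine (41.25% / 25.99%) | 0.0084 | 0.0416 | 0.0166 | 0.0831 |
| Fixed sequence | – | 0.025 | 0 | 0.05 |

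The key-secondary-only column is 0.025 minus P(both significant), and it is the whole excess over 0.025. Two independent tests would give 0.0494, so the correlation removes only part of the inflation.

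**Step 4. Simulation.** One million simulated trials with 311 per arm and unstratified chi-square tests gave, at comparator / esketamine rates: 0.0420 / 0.0413 favouring esketamine, 0.0170 / 0.0166 key secondary only, and 0.0840 / 0.0830 in either direction. The primary alone rejected, two-sided, in 0.0499 / 0.0496 of trials, so its own level is intact.

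**Step 5. Cost of a gate under the planned effects.** Simulated at 311 per arm: primary significant 90.0%, key secondary 85.6%, both 81.4%, key secondary only 85.6 − 81.4 = 4.2%. (The formula in Step 1 gives 85.3% for the key secondary; the difference is immaterial.)

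**The case against.** The strongest reply has three parts.

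First, the plan promises no familywise level. It names one primary endpoint, prints a two-sided 0.05 for each test, and each test meets it. Nowhere does it define success as either endpoint being significant, so the inflation arises only if someone claims a key-secondary-only result. This is true, and it is why the matter does not touch the primary analysis. It does not close the gap, because the text also never says that such a result would not be claimed. Measured against the two-sided 0.05 that the plan does print, the figure for the pair is 8.3% to 8.4%.

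Second, the situation is uncommon: 1.7% of trials under the global null. Estimates and confidence intervals for both endpoints would be reported anyway, so a reader could see that the primary had failed. This limits the weight of the point but does not settle how the result is to be read.

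Third, a gate has a price that the planned-effect calculation does not show. The plan assumes fewer discontinuations after Week 8 on esketamine (10% v 20%). If remission at Week 8 were equal and only that difference were real, a key-secondary-only rejection would be correct. With equal remission assumed at 35% to 41.25%, and 0.63 v 0.56 retained, the key secondary favours esketamine significantly in about 11% to 13% of trials. Under the gate this falls to about 1.8%. That cost is real. Power for this scenario is low even without a gate, and the plan's sample size does not target it. An alpha split would protect it better, but would change the alpha levels on which the sample size rests.

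**Conclusion.** The concern holds. Two separately powered superiority hypotheses are each tested unconditionally at two-sided 0.05, and no rule governs the pair. Under the global null at the plan's rates, the chance of a false claim for esketamine is 4.2% instead of 2.5%, an excess of 1.7 percentage points that consists entirely of key-secondary-only wins. Counting both directions, it is 8.3% to 8.4% instead of 5%.

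The figures rest on the assumed rates, 311 per arm, the nesting of the endpoints, and an unstratified chi-square in place of the planned CMH test, because the documents give no stratum sizes. They hardly depend on which arm's rates serve as the null. The primary analysis stands as planned. The sponsor should close this gap, but it does not undermine the trial's main conclusion.

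**What to change.** State a fixed sequence in SAP Sections 2, 5.3.3 and 5.4.1.3, for example: the key secondary hypothesis is tested at two-sided 0.05 only if the primary is significant at two-sided 0.05 in favour of esketamine; otherwise its p-value is reported as nominal. Make the same statement in Protocol 9.1 and 9.4.2, or list it as a change in SAP Appendix 2.

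The cost is one sentence in three SAP sections plus a protocol edit or one appendix entry. The sample size and both alpha levels do not change. Under the planned effects, the chance of a key secondary claim drops by 4.2 percentage points to 81.4%; the claims lost are correct rejections in trials where the primary misses. If the sponsor already intends this order, the edit only writes it down.

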5.5. Supportive Secondary Endpoint(s)

5.5.1. General Analysis Methods

For continuous/ordinal parameters (eg, MADRS, CGI-S, PHQ-9, EQ-5D-5L, SF-36, SDS, WPAI:D) descriptive statistics of the score or values and change from baseline will be provided for each study visit during the study for the full analysis set. For CGI-C descriptive statistics of the score will be provided for each study visit during the study by study intervention for the full analysis set. Summaries of both observed and last observation carried forward (LOCF) data will be presented. The change from baseline at each visit will be analyzed using a mixed model for repeated measurements based on observed cases. The model will include baseline score as a covariate, and study intervention, stratification factors (age [18 to 64 years (inclusive); 65 to 74 years (inclusive)] and total number of treatment failures [2; 3 or more]), visit, and visit-by-study intervention interaction as fixed effects applying an unstructured covariance matrix. In case of issue with convergence of the model, alternative structures of variance-covariance matrix will be tested. The change from baseline at each visit will also be analyzed using an analysis of covariance model including LOCF data with factors for treatment, stratifications factors (age [18 to 64 years

(inclusive); 65 to 74 years (inclusive)] and total number of treatment failures [2; 3 or more]) and baseline score as a covariate. For all model approaches, LS estimates of the treatment differences at each visit and 95% confidence intervals will be presented. Additionally, for the MMRM model, the LS mean change from baseline averaged over all visits will be presented with 95% confidence interval per treatment group. The corresponding treatment difference will be presented with 95% confidence interval and two-sided p-value.

Additionally, for scales that have a minimum clinically important difference (MCID), the proportion of participants having improved by at least the MCID will be described at each visit and compared between study interventions using CMH chi-square test adjusting for age (18 to 64 years [inclusive]; 65 to 74 years [inclusive]) and total number of treatment failures (2; 3 or more). The same analysis will be conducted for the proportion of participants who deteriorate by at least the MCID.

Time to event parameters (eg, time to improvement by at least MCID) will be analyzed by the Kaplan-Meier method and study interventions will be compared using a 2-sided log-rank test for the full analysis set. Time to event will be summarized with median, 25th and 75th percentile (if estimable). Confidence intervals of 25th, 50th, and 75th percentile of time to event will also be provided. Hazard ratios and their confidence intervals will be estimated using Cox proportional hazard models stratified by age (18 to 64 years [inclusive]; 65 to 74 years [inclusive]) and number of previous treatment failures (2; 3 or more).

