A total of 622 participants will be randomly assigned on Day 1 (baseline) in a 1:1 ratio to 1 of 2 open-label study intervention arms (311 participants per arm). The randomization will be balanced by using randomly permuted blocks and will be stratified by age (18 to 64 years [inclusive]; 65 to 74 years [inclusive]) and total number of treatment failures (2; 3 or more [inclusive of current antidepressive treatment at screening used to determine eligibility]).

Esketamine arm

Participants will continue to take their current SSRI/SNRI in combination with esketamine nasal spray.

On Day 1, participants will have their first nasal treatment session. Adult participants aged 18 to 64 years will start with a dose of 56 mg. Elderly participants aged 65 to 74 years and adults of Japanese ancestry will start with a dose of 28 mg. As of Day 4, the dose may be increased from 56 mg to 84 mg in adult participants, from 28 mg to 56 mg in elderly participants and adults of

Japanese ancestry, or participants may remain at the starting dose, as determined by the investigator based on efficacy and tolerability. Elderly participants and adults of Japanese ancestry may be uptitrated in 28 mg increments at subsequent visits. The highest dose that may be used in all participants is 84 mg. Nasal treatment sessions will occur twice weekly during Week 1 to Week 4, once weekly during Week 5 to Week 8, and once weekly or every 2 weeks, as determined by the investigator based on efficacy and tolerability, during the maintenance phase (Week 9 to Week 32). Dosing may be increased at any visit, may remain the same, or may be reduced as determined by the investigator based on efficacy and tolerability. Nasal treatment sessions should not take place on 2 consecutive days. Esketamine nasal spray dosing and related safety-monitoring procedures MUST be performed LAST at all visits. Esketamine nasal spray must NOT be administered before all other visit assessments are completed. Food will be restricted for at least 2 hours before each administration of esketamine nasal spray at each session.

Comparator Arm

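### For the supportive time-to-event endpoints, the log-rank test names no strata while the Cox model is stratified by the randomisation factors, so the p-value and the hazard-ratio interval do not correspond

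*SAP*

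**What the plan says.** SAP 5.5.1 (General Analysis Methods) sets out the time-to-event analysis in one paragraph. Its scope is given by example: "Time to event parameters (eg, time to improvement by at least MCID) will be analyzed by the Kaplan-Meier method". The arms are then compared as follows: "study interventions will be compared using a 2-sided log-rank test for the full analysis set". No stratification factor is attached to that test. The estimate comes next: "Hazard ratios and their confidence intervals will be estimated using Cox proportional hazard models stratified by age" and by number of treatment failures (2; 3 or more). The protocol pairs the test and the model in the same way in its synopsis (1.1) and in 9.4.2.

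The strata in the Cox model are the randomisation strata. SAP 1.2 says: "The randomization will be balanced by using randomly permuted blocks and will be stratified by age" and by total number of treatment failures, counting the current treatment. The other between-arm analyses in SAP 5.5.1 also use both factors: the MMRM, the ANCOVA, and the MCID proportions, which are "compared between study interventions using CMH chi-square test adjusting for age" and number of treatment failures.

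Time to relapse is treated separately. SAP 5.5.3 gives only Kaplan-Meier summaries, and SAP Appendix 2 (6.2) explains that "since time to relapse is an exploratory endpoint, the analysis of this endpoint will only be descriptive".

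**The concern.** A p-value and a hazard-ratio confidence interval printed side by side are normally read as two views of one analysis. The test that belongs with a stratified Cox model is its score test, which (apart from the handling of ties) is the log-rank test stratified by the same factors. Here the p-value would compare the arms over all participants pooled, while the interval would come from comparisons within strata. The two can fall on opposite sides of 0.05, and the SAP does not say which one governs.

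There is also a question of efficiency. Stratified randomisation balances the strata across arms, but the pooled log-rank variance takes no credit for that balance. If the strata are prognostic, the pooled test rejects less often than it should under the null and loses some power under the alternative. The contrast is plainest for MCID improvement: the proportion improved is tested with adjustment, and the time to that improvement without.

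**Working it through.** **1. The plan's own figures.** The only sample sizes stated are for the two binary endpoints. With n per arm = [z(0.975)·√(2·p̄·q̄) + z(power)·√(p1·q1 + p2·q2)]² / (p1 − p2)², where q = 1 − p and p̄ is the mean of p1 and p2:

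- Primary: p1 = 0.50 × 0.825 = 0.4125 and p2 = 0.35 × 0.825 = 0.28875, power 90%. n = (1.3226 + 0.8575)² / 0.12375² = 310.4, so 311.
- Key secondary: p1 = 0.4125 × 0.70 × 0.90 = 0.2599 and p2 = 0.28875 × 0.70 × 0.80 = 0.1617, power 80%. n = (1.1305 + 0.4819)² / 0.098175² = 269.8, so 270.

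Both match. Neither depends on the log-rank wording. No event count, hazard ratio or power is stated for any time-to-event endpoint.

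**2. The two tests.** In each stratum k, let O_k be the observed and E_k the expected events in the esketamine arm, and V_k the hypergeometric variance. The stratified statistic is (Σ(O_k − E_k))² / ΣV_k. The unstratified statistic computes O, E and V once on the pooled data. Each is compared with 3.84.

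**3. Simulation inputs.** From the documents: 622 participants, 1:1 allocation within four strata, and follow-up to Week 32, with visits taken as 2-weekly. Assumed, because the documents give no figures:

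- 15% aged 65 to 74 and 40% with 3 or more failures; the smallest stratum then has about 622 × 0.15 × 0.40 = 37 participants;
- comparator event probability by Week 32 in the reference stratum of 45% or 80%, that is, weekly hazards of −ln(0.55)/32 = 0.0187 and −ln(0.20)/32 = 0.0503;
- 25% dropout by Week 32;
- treatment hazard ratio for improvement of 1.3 or 1.4;
- stratum hazard ratios (age 65 to 74; 3 or more failures) from 1.0 down to 0.4.

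There were 4,000 trials per setting, so the standard error is at most √(0.25/4000) = 0.8 points per figure.

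**4. Power, unstratified vs stratified (%).**

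| Stratum HRs (age; failures) | 45%, HR 1.3 | 45%, HR 1.4 | 80%, HR 1.3 | 80%, HR 1.4 |
|---|---|---|---|---|
| 1.0; 1.0 (none) | 56.8 vs 57.2 | 80.1 vs 79.9 | 81.7 vs 81.7 | 95.4 vs 95.6 |
| 0.8; 0.7 (modest) | 49.7 vs 50.1 | 74.8 vs 75.2 | 75.4 vs 77.0 | 93.6 vs 94.0 |
| 0.6; 0.5 (strong) | 46.1 vs 48.1 | 67.7 vs 69.8 | 69.6 vs 74.7 | 89.8 vs 92.3 |
| 0.4; 0.4 (very strong) | 42.6 vs 46.1 | 63.5 vs 67.6 | 61.6 vs 70.0 | 83.8 vs 89.4 |

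The loss from not stratifying is within simulation error for non-prognostic strata, 0.4 to 1.6 points for modest effects, 2.0 to 5.1 for strong and 3.5 to 8.4 for very strong.

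**5. Type I error (treatment HR 1.0).** Unstratified 3.4% to 5.2%; stratified 4.8% to 5.2%. The lowest unstratified value comes from very strong strata with 80% events.

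**6. Disagreement.** Two tests run on the same trials must disagree in at least the share by which their rejection rates differ. In the strong, 80%, HR 1.3 setting that is at least 74.7 − 69.6 = 5.1% of trials.

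**The case against.** The best defence has four parts.

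*The pairing is legitimate.* A pooled log-rank test compares the Kaplan-Meier curves that are displayed, and the stratified Cox model supplies an estimate within strata. The test is valid. This stands: nothing here invalidates the p-value. It does not explain why this is the one between-arm test in SAP 5.5.1 without the randomisation factors.

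*The text is silent, not explicit.* The word unstratified never appears, and the strata are named later in the same paragraph. A reader might infer that the sponsor deliberately chose an unstratified test; the documents do not show that. But a programmer following the sentence would run the test without strata, and nothing elsewhere corrects this.

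*The scope is narrow.* A reader might infer that every time-to-event endpoint is affected. SAP 5.5.3 and Appendix 2 rule that out, because time to relapse gets neither a log-rank test nor a Cox model. What remains is one example, time to MCID improvement. The scale sections of the SAP define no such variable and give no MCID value, although protocol 9.4.2 says the SAP will document the MCIDs. This stands and limits the point.

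*Lost power is conditional.* A reader might infer that power is certainly lost. The documents give no figure for how prognostic the strata are, and if they are not prognostic the loss is nil. This also stands.

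**Conclusion.** The point holds in a limited form. For the supportive time-to-event endpoints under SAP 5.5.1, the log-rank p-value and the Cox interval come from unmatched analyses. That rests on the text alone and needs no assumption.

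The effect on power is conditional. Its size (nil, under 2 points, or about 2 to 8 points) depends wholly on the assumed stratum shares, event rates and stratum effects listed above, and more than about 5 points needs very strong prognostic effects.

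Two stronger conclusions would be wrong. The unstratified test does not inflate type I error; where it departs from 5% it is conservative. Nor does it touch the trial's main claims: the primary and key secondary endpoints are tested by CMH adjusted for both factors (SAP 5.3.3 and 5.4.1.3), and these are the only powered analyses. This is a minor but free improvement.

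**What to change.** In SAP 5.5.1, specify a 2-sided log-rank test stratified by age group (18 to 64; 65 to 74) and total number of treatment failures (2; 3 or more), with the same strata for the Cox model.

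In the same edit:

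- Use one name for the second factor. The Cox sentence speaks of previous failures, while the randomisation factor counts the current treatment as well.
- State that the strata come from CRF data for both the test and the model. SAP 5.3.3 and 5.4.1.3 settle CRF (main) against IXRS (sensitivity) only for the CMH tests.
- Record the change from protocol 1.1 and 9.4.2 in SAP Appendix 2, which at present lists only the time-to-relapse change.

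The cost is one phrase, two clarifications and one appendix entry. No new data are needed, and in the simulations stratifying cost nothing beyond simulation error when the strata were irrelevant.
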